9.2.3 Suspected unexpected serious adverse reactions (SUSARs)

Not applicable.

9.3 Annual safety report

Not applicable.

9.4 Follow-up of adverse events

All AEs will be followed until they have abated, or until a stable situation has been reached. Depending on the event, follow up may require additional tests or medical procedures as indicated, and/or referral to the general physician or a medical specialist. SAEs need to be reported till end of study within the Netherlands, as defined in the protocol.

9.5 Data Safety Monitoring Board (DSMB)

The independent Data and Safety Monitoring Board (DSMB) is responsible for the oversight review of all AEs. The DSMB will include leading experts in interventional cardiology/cardiology, vascular medicine, pulmonology and biostatistics not participating in the study. During the course of the study, the DSMB will review accumulating safety data to

Version 2.1: 16-12-2024

monitor the incidence of adjudicated events and other trends that would warrant modification or termination of the study. Responsibilities, qualifications, membership, and committee procedures are outlined in the DSMB Charter.

Data will be supplied to and reviewed by the DSMB in unblinded fashion. Any DSMB recommendations for study modification or termination because of concerns over subject safety or issues relating to data monitoring or quality control will be submitted in writing to the Executive Committee for consideration and final decision. However, if the DSMB at any time determines that a potentially serious risk exists to subjects in this study, the DSMB chairperson will immediately notify both the sponsor and the Lead Investigators. Should the sponsor decide not to fully implement the advice of the DSMB, the sponsor will send the advice to the reviewing METC, including a note to substantiate why (part of) the advice of the DSMB will not be followed.

10. STATISTICAL ANALYSIS

The data will be analyzed on an ITT basis in several steps. The ITT populations consist of all subjects who have been randomized, i.e. when the subject number and allocated regimen are recorded in the eCRF. Patients will be analyzed in accordance with the randomized treatment assignment irrespective of the factual implementation of the assigned treatment regimen. The baseline characteristics in each trial arm will be described. Continuous variables will be described as mean with standard deviation (SD) or median with interquartile range (IQR) for continuous variables depending on their normality of distribution. The Shapiro–Wilk test will be used to assess normality. Categorical variables are presented as numbers and percentages. On top of the ITT analyses a per-protocol (safety population) analysis will be performed. A detailed description of the statistical analysis will be provided in the Statistical Analysis Plan.

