Intervention: The intervention consists of immediate thrombectomy (FlowTriever, Inari Medical or Indigo, Penumbra Inc.) without systemic/locally administered thrombolysis. Thrombectomy is performed via jugular or femoral venous access by an interventional cardiologist, interventional radiologist or vascular surgeon according to the instructions for use (IFU) for the particular device. The catheter is advanced over a preplaced guidewire across the right heart into the pulmonary arteries to the location of proximal thrombus. Procedural therapeutic anticoagulation with heparin is administered. After removal of the dilator, the thrombus is extracted by controlled volume aspiration through an aspiration catheter using a syringe or dedicated aspiration system, with multiple aspirations performed as needed. Procedural objectives will be clearly stated prior to the intervention and patient's clinical and hemodynamic status and residual thrombus will guide the investigators to determine when to terminate the procedure. Treatment success is defined as clear evidence of right ventricular Version 2.1: 16-12-2024

recompensation. The procedure must be discontinued in case of treatment failure, i.e. lack of improvement or hemodynamic deterioration, and major CDT complications such as cardiac arrest or severe haemoptysis. Complications will be solved directly, with a procedure/treatment best suitable according to the treating physician, to minimalize the risk of damage and promote patient recovery.

Main study parameters/endpoints: The primary outcome is the 30-day composite incidence of the binary endpoints of

- 1) all-cause mortality
- 2) treatment failure
- 3) major bleeding
- 4) and all-cause stroke

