8. METHODS

8.1 Study parameters/endpoints

8.1.1 Main study endpoint

The primary outcome is the composite incidence of the binary endpoints of all-cause mortality, treatment failure, major bleeding and all-cause stroke at day 30.

Treatment failure in the first six hours after randomization is defined as life-threatening hemodynamic or respiratory deterioration. This deterioration is the clinical scenario if, following randomisation, the patient develops overt cardiorespiratory instability over at least 15 minutes necessitating CPR, escalation of respiratory support, or ECMO. After these first six hours, treatment failure will also be defined by increasing dosages of cardiorespiratory support (e.g. oxygen, catecholamines), and lack of improvement. Lack of improvement is defined by the presence of at least one of the following criteria: i) an equal or rising SCAI SHOCK stage (**Table 1**), ii) an equal or rising Fraction of Inspired Oxygen (FiO₂) level to maintain adequate oxygen saturation (i.e. \geq 92%), or iii) an equal or decreasing P/F ratio. Treatment failure will be determined every 6 hours starting at the moment of randomisation, until the patient is considered stable and transferable to the ward.

Upon establishing the outcome 'treatment failure' physicians are allowed to escalate therapy in whatever way they consider appropriate. Therapy crossover without meeting the primary outcome is not allowed. Major bleeding is defined as Bleeding Academic Research Consortium (BARC)3b and BARC3c bleeding (=intracranial haemorrhage).²¹ Ischemic stroke is defined as any stroke (National Institutes of Health Stroke Scale \geq 1).

All primary study outcomes will be adjudicated by an independent critical events committee. This committee will consist of an independent group of three individuals with pertinent expertise that reviews and adjudicates important endpoints and relevant AEs reported by study investigators. The committee will be blinded to treatment assignment and review safety event dossiers, which may include copies of subject source documents provided by study sites, for all reported cases where the primary outcome was met. Committee members may include (interventional) cardiologists, intensivists, pulmonologists, vascular medicine specialists, and (interventional) radiologists, as well as other experts with the necessary therapeutic and subject matter expertise to adjudicate the event categories outlined above.

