8.6 Follow-up of subjects withdrawn from treatment

The primary outcome will be assessed following the principles of intention to treat (ITT). Hence, if the reperfusion treatment to which the patient is allocated to receive is not provided, the patient will still be followed for the occurrence of primary and secondary outcomes.

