10.2 Secondary study parameter(s)

For continuous secondary endpoints (e.g., DOOR in the first 7 days after randomization), we will estimate mean or median difference between trial arms using an Independent Samples t

Test (mean difference) or a Mann Whitney-U test (median difference), depending on the normality of the distribution. Regarding categorical secondary outcomes, differences between the trial arms will be analyzed using a Chi-square test or Fisher's exact test, when appropriate. Repeated measures secondary outcomes are analyzed using mixed-effects (longitudinal) regression models. Outcomes will be (numerically) stratified according to the type of thrombectomy (FlowTriever vs. Indigo). A per-protocol analysis is performed as a sensitivity analysis. Both R studio and Graphpad software will be used for statistical analysis and making graphs, respectively. A two-sided p-value <0.05 is considered statistically significant. Missing data, where applicable, will be imputed with the use of multiple imputation under the missing-at-random assumption with chained equations. Outcome variables will not be imputed, as is the convention in randomized controlled trials. Patient safety will be monitored by a Data Safety Monitoring Board (DSMB) that will include several senior researchers. Subgroup analyses will be performed (if feasible, i.e. if numbers per subgroup are sufficiently large) for man versus women, age below 75 or 75 and older, different devices used and subtype of high-risk PE.

A cost effectiveness analysis (CEA) will be performed after a time horizon of one year for the primary outcome and QALYs. QALYs will be estimated using the EQ-5D-5L administered at day 7 and after 3, 6, 9 and 12 months, the Dutch tariff, and the "Area under the Curve" approach.^{28,29}

The economic evaluation will be performed in accordance with the 'Dutch Guideline for economic Evaluations'.¹⁸ In the main analysis, the societal perspective will be applied, meaning that all costs will be included irrespective of who pays or benefits (i.e. the cost of the intervention, other healthcare use, informal care, as well as productivity losses from unpaid and paid work). Intervention costs will be micro-costed, all other costs will be measured using cost questionnaires administered at 7 and after 3, 6, 9 and 12 months, and valued using standard prices provided by the 'Dutch Manual for Costing Studies in Health Care'.³⁰

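### Protocol Section 10 labels the per-protocol set as the safety population, although these are two different analysis sets and Section 10.2 gives the per-protocol analysis only a sensitivity role

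*Protocol*

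**What the plan says.** Section 10 defines the main population as all randomised patients: "The ITT populations consist of all subjects who have been randomized, i.e. when the subject number and allocated regimen are recorded in the eCRF". The analysis rule is strict: "Patients will be analyzed in accordance with the randomized treatment assignment irrespective of the factual implementation of the assigned treatment regimen". It then adds a second set under a double name: "On top of the ITT analyses a per-protocol (safety population) analysis will be performed". Section 10.2 mentions the per-protocol set again, this time without the safety label: "A per-protocol analysis is performed as a sensitivity analysis". Later in Section 10.2 it appears among the sensitivity analyses of the economic evaluation.

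Three further places bear on who might count as a deviator.

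- Section 8.6 foresees that the allocated reperfusion may not be given, and says that "the patient will still be followed for the occurrence of primary and secondary outcomes".
- The Intervention paragraph of the Summary requires catheter-directed thrombectomy (CDT) to be stopped in stated circumstances: "The procedure must be discontinued in case of treatment failure, i.e. lack of improvement or hemodynamic deterioration, and major CDT complications such as cardiac arrest".
- Section 8.1.1 lets physicians escalate as they see fit once treatment failure is established, and otherwise rules out switching: "Therapy crossover without meeting the primary outcome is not allowed".

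Section 9.2.2 lists the study-specific SAEs: vessel laceration, haemothorax, tamponade, valve injury and pneumothorax. None of these is named as a primary endpoint in Section 8.1.1 or a secondary endpoint in Section 8.1.2.

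**The concern.** The two terms describe sets built for different questions. A per-protocol set asks what happens when treatment goes as planned, so it leaves out patients for whom it did not. A safety set asks what happened to everyone exposed to a treatment, so it must keep them. Using one set for both purposes means that inclusion in the safety summary can depend on how the treatment went, which is partly what a safety summary should report.

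What is at stake is limited. The efficacy and main harm comparisons rest on the ITT population and do not change. The exposed part is the tabulation of procedural harms that are not ITT endpoints. For these, the only set in the protocol that carries the word safety is the per-protocol set. There is also a gap at the other end: a patient allocated to CDT who receives only thrombolysis is counted under CDT in the ITT analysis and may be absent from a per-protocol set. Neither named set then clearly shows harm by the treatment actually received.

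**Working it through.** The plan gives no figure on this point, so the first check is to set the populations side by side. The per-protocol column assumes an ordinary rule that excludes deviators, because the protocol gives no membership rule. The last column is a conventional safety set.

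| Patient | ITT (Section 10) | Per-protocol, ordinary rule | Safety set by treatment received |
|---|---|---|---|
| CDT completed, complication occurs | CDT | in | CDT |
| CDT stopped for a complication, as the Summary requires | CDT | depends on the rule | CDT |
| CDT stopped, treatment failure established, thrombolysis then given | CDT | depends on the rule | received both, shown separately |
| Allocated CDT, never started, thrombolysis given | CDT | out | thrombolysis |
| Both treatments given, switch made without the primary outcome being met | as allocated | out | received both, shown separately |
| Neither treatment started | as allocated | out | out |

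The per-protocol and safety columns agree with certainty only in the first and last rows. In rows four and five they differ under any ordinary rule. In rows two and three the answer depends on whether protocol-directed stopping and permitted escalation count as deviations. So the two names cannot denote one set.

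The second check is which harms are exposed.

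- Death, treatment failure, BARC3b/3c bleeding and stroke are components of the primary outcome (Section 8.1.1) and secondary endpoints (Section 8.1.2). Both are analysed by ITT.
- The SAEs listed in Section 9.2.2 are not endpoints. They are the ones that would naturally be tabulated in a safety population.

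The third check is whether a size can be given. Inputs: 74 CDT patients (Section 4.4); 22.6% device-related complications and 3.8% bailout in the high-risk FlowTriever cohort (Section 1).

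- Complications: 0.226 × 74 = 16.7, about 17. Rate 17/74 = 23.0%.
- Bailouts: 0.038 × 74 = 2.8, about 3.

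Suppose, for illustration only, that the 3 bailout patients were excluded, leaving 74 − 3 = 71. The result depends on how many of them are among the 17:

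- all 3: 14/71 = 19.7%
- 2: 15/71 = 21.1%
- 1: 16/71 = 22.5%
- none: 17/71 = 23.9%

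The overlap is not reported, and the change runs from −3.3 to +0.9 percentage points. The 22.6% also consists of haemoglobin decrease, access-site haemorrhage and hypotension, not the SAEs of Section 9.2.2. In addition, Section 4.4 suggests that bailout may correspond to this trial's treatment failure, after which escalation is allowed, so these patients need not be deviators at all. The example shows only that neither size nor sign is fixed by the document.

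**The case against.** The strongest reply is that this is a slip of wording with no demonstrated consequence. No section says that aborted or switched procedures are dropped, or that safety is summarised only in this set. The parenthesis could have been meant as an as-treated set. The analysis comes on top of ITT, which covers the main harms. All spontaneously reported or observed adverse events are recorded (Section 9.2.1), and the data safety monitoring board reviews all of them (Section 9.5). Section 10 also defers detail to the statistical analysis plan, so the absence of a membership rule is not a fault.

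Most of this stands. A reader might infer that safety will be reported after removing aborted and crossed-over CDT procedures, that these are the patients with complications, and that the result will favour CDT. The document does not support that reading. Stopping for a major complication is required by the Summary, and escalation after treatment failure is permitted by Section 8.1.1, so a patient managed that way has followed the protocol. Lack of improvement is also a reason to stop, so not every aborted case is a complication. The illustrative shift can go either way.

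The reply does not rescue the label itself. The fault is a statement that is present, not a detail that is absent: the analysis plan could separate the two sets only by departing from the protocol's sentence. If an as-treated set was meant, then per-protocol is the wrong term for it. Board review during the trial does not settle the population for the final tables.

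**Conclusion.** The point holds as an error in naming and separating analysis sets. Section 10 equates the per-protocol set with the safety population, while Section 10.2 uses the per-protocol analysis for sensitivity only. If the label is followed, patients who did not receive or complete their allocated reperfusion, or who switched, could be left out of the summary of procedural harms that are not ITT endpoints.

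The conclusion rests on two assumptions: that per-protocol has its usual meaning, and that the study-specific SAEs would be tabulated in the set called safety population. It does not rest on any claim that such patients will be excluded or that CDT will gain from it. The size and direction of any bias cannot be derived. The primary comparison and the ITT analyses of death, treatment failure, major bleeding and stroke are unaffected. It is worth correcting because the correction is cheap and leaves less room for choosing the safety population after the data are known.

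**What to change.** In Section 10, delete the parenthesis from the per-protocol sentence and define two sets.

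- **Safety set:** every patient in whom either reperfusion treatment was started, analysed by treatment received, with patients who received both shown separately. Use it for the study-specific SAEs of Section 9.2.2 and other adverse-event tables.
- **Per-protocol set:** kept for the sensitivity analyses already stated in Section 10.2, including those of the economic evaluation. State that stopping or escalation permitted by the protocol is not a deviation. The remaining membership rules can stay in the statistical analysis plan.

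There is no reason to confine the per-protocol set to the primary endpoint; that would remove uses the protocol already gives it. The cost is one sentence and one extra set of safety tables. The ITT analyses, the sample size and the data collected do not change.

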10.1 Primary study parameter(s)

For the primary composite endpoint, we will provide the cumulative incidence (number and percentage) for each trial arm and estimate the Odds Ratio (OR, including the 95% Confidence Interval using a binary logistic regression) to compare trial arms. In case of imbalance in background characteristics we can adjust the logistic regression analysis for the respective confounders.

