3. STUDY DESIGN

TORPEDO-NL will be an investigator-initiated, academically sponsored, multicentre, openlabel, randomized controlled trial (RCT) to show superiority of CDT (2 commercially available systems; technical variant) on top of regular anticoagulation over systemic thrombolysis plus regular anticoagulation in patients with high-risk PE in the Netherlands. A 2:1 (thrombectomy: systemic thrombolysis) randomization will be applied. The randomization procedure will be web-based, using randomly sized blocks consisting of 3,6 or 9 patients. Randomization will occur after the verification that a thrombectomy procedure can be started (randomisation-toneedle time) within 60 minutes. Randomization will be stratified by centre. Patients will be followed for 1 year after randomisation. The primary outcome will be assessed after a 30-day follow-up period (**Figure 1**). The inclusion is estimated to take 2.5 years. Finally, all primary study outcomes will be adjudicated, blinded, by an independent critical events committee, a more detailed description will be provided in paragraph 8.1.1.

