To assess statistical power, the probability of the primary outcome was assumed to be 0.19 in the thrombectomy arm (based on the most recent data available) and 0.46 in the systemic thrombolysis arm (corresponding with a treatment OR of 3.71 and a risk difference of 27.5%; number needed to treat 3.6). The minimum clinically important difference was set at 27.5% based on discussion within the project group, scientific societies and patient representatives, and on clinical relevance for the difference facets of the composite endpoints. The assumed ARR of 27.5% consists of 5% decrease in mortality, 21.5% reduction in treatment failure or major bleeding and 1% reduction in ischemic stroke (the latter both based on expert opinion).¹⁸ Given a power of 80%, a two-sided α -level of 5%, and a 1:2 (systemic thrombolysis:CDT) patient allocation, 35 patients are needed in the systemic thrombolysis and 70 patients in the CDT arm. Assuming 5% drop-out, 37 patients (systemic thrombolysis) and 74 patients (CDT; total 111 patients) will be recruited. The calculation was done using G*Power (version 3.1.9.6) and is based on proportion difference tested with an anticipated OR.

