8.2 Randomization, blinding and treatment allocation

A 2 (CDT: systemic thrombolysis) :1 (TT) randomisation will be applied. The randomization procedure will be web-based (castor), using randomly sized blocks consisting of 3,6 or 9 patients. Randomization will occur after the verification that a thrombectomy procedure can be started (randomisation-to-needle time) within 60 minutes. Randomization will be stratified by centre.

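### Randomisation is stratified by centre but the primary logistic regression has no centre term, so the test is conservative if centres differ in event risk

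*Protocol*

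**What the plan says.** On the design, section 3 of the protocol states "A 2:1 (thrombectomy: systemic thrombolysis) randomization will be applied", "using randomly sized blocks consisting of 3,6 or 9 patients". Section 8.2 adds "Randomization will be stratified by centre"; the Summary and section 3 say the same. No other stratification factor is named.

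On the analysis, section 10.1 gives the cumulative incidence per arm and will then "estimate the Odds Ratio (OR, including the 95% Confidence Interval using a binary logistic regression) to compare trial arms". Its one rule on covariates is: "In case of imbalance in background characteristics we can adjust the logistic regression analysis for the respective confounders". Centre is not mentioned. Section 10 leaves a detailed description to a statistical analysis plan that is not at hand. Section 10.2 allows for clustered data by a mixed model, but only for the economic evaluation and only if applicable.

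On the sample size, section 4.4 states that "the probability of the primary outcome was assumed to be 0.19 in the thrombectomy arm" and "0.46 in the systemic thrombolysis arm (corresponding with a treatment OR of 3.71 and a risk difference of 27.5" per cent. "Given a power of 80%, a two-sided α -level of 5%, and a 1:2 (systemic thrombolysis:CDT) patient allocation", it needs 35 + 70 patients, and 37 + 74 = 111 after 5% drop-out. Centre plays no part in that calculation.

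**The concern.** Permuted blocks within centre make the arms alike in centre mix. Part of the variation between patients can then no longer reach the treatment comparison. A model that leaves centre out does not know this: its standard error still allows for between-centre variation that the design has removed. The test then rejects too rarely under the null, and the interval covers its target more often than 95%.

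The rule in 10.1 does not cure this. It asks whether a characteristic is imbalanced, and centre is the one factor that the design keeps close to balance.

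Centres could well differ in risk. From six hours on, treatment failure depends on oxygen and catecholamine dosing, FiO2 and P/F ratio (section 8.1.1), which partly reflect local intensive care practice. What is at stake is power in a trial with about 37 × 0.465 + 74 × 0.19 = 17.2 + 14.1 ≈ 31 expected events.

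**Working it through.** **1. The plan's own figure.** Two-sided test of two proportions, 0.46 v 0.19, allocation 1:2, 80% power.

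- Pooled variance, with mean risk (0.46 + 2 × 0.19)/3 = 0.28: n(control) = [1.96 × √(1.5 × 0.28 × 0.72) + 0.842 × √(0.46 × 0.54 + 0.19 × 0.81/2)]² / 0.27² = 33.3, so 34 + 68 = 102.
- Unpooled variance: 35.03 in the control arm.
- Fisher's exact test with 35 + 70: power 79.1% at 0.46 and 80.5% at 0.465.
- Drop-out: 35/0.95 = 36.8 and 70/0.95 = 73.7, so 37 + 74 = 111.

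The stated size reproduces. The printed odds ratio of 3.71 and difference of 27.5% correspond to 0.465 rather than 0.46, a rounding matter with no bearing here; 0.465 is used below.

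**2. Inputs that the protocol does not give.** The number of centres is assumed to be 6 to 15. The between-centre SD on the logit scale is assumed to be 0, 0.5, 1.0 or 1.5. Around a 28% event rate, centres one SD below and above the middle then have 19% and 39% (SD 0.5), 13% and 51% (SD 1.0), or 8% and 64% (SD 1.5).

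**3. Simulation.** N = 111, 2:1, random blocks of 3, 6 or 9 within centre, 4,000 to 6,000 runs per setting. Model: logit P(event) = α(arm) + u(centre), with α set so that the marginal risks are 0.28 in both arms (null) or 0.465 v 0.19. Two tests are compared:

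- Unadjusted Wald: z = log OR / √(1/a + 1/b + 1/c + 1/d).
- Stratified Mantel-Haenszel: z = Σ(a_k − n1_k e_k/n_k) / √Σ[n1_k n0_k e_k (n_k − e_k) / (n_k²(n_k − 1))], summed over centres k.

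| SD | Type I, unadjusted | Type I, stratified | Power, unadjusted | Power, stratified |
|---|---|---|---|---|
| 0 | 4.2–5.1% | 4.4–5.4% | 84–86% | 84–86% |
| 0.5 | 3.7–4.5% | 4.4–5.5% | 85–86% | 86–87% |
| 1.0 | 2.8–3.6% | 4.7–5.5% | 86–87% | 89–91% |
| 1.5 | 1.6–2.7% | 4.4–5.5% | 86–88% | 92–94% |

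Type I error is for 6, 10 and 15 centres; power is for 6 and 10. Monte Carlo error near 5% is about √(0.05 × 0.95/6000) = 0.3 points. Further runs at SD 1.0 with 8 or 15 centres gave 2.9–3.7% for the unadjusted test and power gains of about 2 to 3 points. With 15 centres and no centre effect, the stratified test lost 1 to 1.4 points.

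**4. Why the test is conservative.** Under the null with 10 centres, the true spread of the unadjusted log OR against its mean model standard error is 0.469 v 0.459 at SD 0, 0.443 v 0.466 at SD 1.0, and 0.431 v 0.472 at SD 1.5. At the design alternative, with 6 and 10 centres, coverage of the unadjusted 95% interval for the marginal OR is 95.0%, 95.1–95.2%, 96.8–97.1% and 97.9–98.0% at SD 0, 0.5, 1.0 and 1.5.

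**5. Where the power gain comes from.** With 8 centres and SD 1.0, the median 95% interval on the log-OR scale is 1.77 wide unadjusted and 2.02 wide for Mantel-Haenszel. The mean log OR moves from −1.37 (OR 3.9) to −1.61 (OR 5.0). Dividing the widths by 3.92 gives standard errors of 0.452 and 0.515, so estimate over standard error goes from 1.37/0.452 = 3.03 to 1.61/0.515 = 3.12. The interval widens, but the conditional OR moves further from 1 than the interval grows.

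**6. Choice of method.** With 8 centres, a random intercept had type I error 5.0% (SD 0) and 4.7% (SD 1.0), and power 85.5% and 88.7%, against 85.2% and 85.7% for the unadjusted Wald test. An unadjusted likelihood-ratio test at SD 1.0 had 3.6% and 85.7%, so the power gain comes from including centre and not from the type of test. Logistic regression with a fixed effect per centre reached 6.1% type I error with 10 centres.

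**The case against.** **The protocol does not exclude centre.** A reader might infer that it does. It does not say so, and the analysis plan could add a centre term. But 10.1 is not silent either: it names the effect measure, the model and the condition for adjustment. Adding centre regardless of imbalance would go beyond that condition, so the point concerns what the protocol fixes.

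**The interval would not get narrower.** A reader might infer that accounting for centre buys a tighter interval. Step 5 shows the opposite on the log-OR scale. Conditioning on centre changes the target from a marginal to a conditional OR. This objection stands, and the remedy must name its target.

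**The size rests on assumptions.** Nothing in the protocol supports an SD of 1.0, and the simulated unadjusted test keeps about 84% power or more with 111 patients, above the 80% target. This also stands.

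**Some sources of centre variation are not addressed.** Device and operator act only in the thrombectomy arm. That is a treatment-by-centre effect, which neither a random intercept nor a common OR handles. The argument has to rest on differences in underlying risk and local care.

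**Balance is not exact.** With 15 centres there are about 111/15 = 7.4 patients each, and incomplete blocks can leave some imbalance. The 10.1 rule would therefore rarely, rather than never, bring centre in.

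**The random intercept was checked with 8 centres only.** That it has no cost elsewhere is not shown.

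**Conclusion.** The mismatch between design and analysis is real and its direction is clear: if centres differ, the planned test is conservative. At an assumed SD of 1.0, type I error is about 3 to 4% and about 2 to 4 points of power are given up. At 0.5 the power change is at most about 1.6 points, and with no centre effect nothing is lost. These figures depend on a number of centres and a heterogeneity that the protocol does not give.

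A reader might infer that the primary result would be invalid or prone to false positives. The documents and the calculations do not support that: the error runs in the safe direction and the stated sample size stands. This is an inexpensive improvement to make before analysis.

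**What to change.** In 10.1, and in the analysis plan to match, state the following.

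- The primary test accounts for centre whatever imbalance is observed. Choose one method in advance: logistic regression with a random intercept for centre, or a Mantel-Haenszel analysis stratified by centre with a rule for pooling very small centres that is set before unblinding. Do not use a fixed effect per centre.
- The resulting OR is conditional on centre.
- The crude percentages per arm and the unadjusted (marginal) OR are reported alongside.

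This takes a few sentences, no new data and no change in sample size. The downside is about 1 point of power with Mantel-Haenszel if there are many centres and no centre effect, and a conditional OR whose log-scale interval is somewhat wider than the crude one (about 2.0 to 2.1 against 1.77 at SD 1.0).
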